| Subject satisfaction questionnaire  |   |   |  |  |   |   |  | X |   | X d |
| Safety visit question   |   |   |  |  |   | X |  |   | X |                |
| Adverse Events e   | X | X |  |  | X | X |  | X | X | X              |
| Concomitant Therapies/Procedures d   |   | X |  |  | X | X |  | X | X | X              |
| Subjects with Complete Response evaluation and IC for continuation into long-term follow-up study |   |   |  |  |   |   |  |   |   | X              |
| Exit Form f  |   |   |  |  |   |   |  |   |   | X              |

- a) Visits 2 and 4 may be delayed for up to 2 weeks in case of unsuitable weather conditions at randomization/treatment outset. These postponements will be automatically added to the time of scheduled Visits 5 and 6
- b) If subjects experience rain during the 2 hours of daylight exposure of either DL-PDT visit, they will be instructed to go indoors at the investigative site and the study drug will be washed off. The treatment will be considered incomplete and should be repeated at a minimum interval of 2 weeks, with a maximum interval of 4 weeks. There will be only one attempt at retreatment of an incomplete treatment. These visits will be Visits 2b and 4b. If the attempt at retreatment is also incomplete, the subject will continue in the study. Likewise these repeat visits will be added to the time of scheduled Visits 5 and 6.
- c) Only for females of childbearing potential, urine at Visits 1, 2, 2b (if applicable), 4, 4b (if applicable) and 6
- d) Should be performed earlier if subject discontinues before Visit 6
- e) Adverse Events have to be collected from the time of the Informed Consent signature
- f) Exit form should be completed after subject data collection has been completed for subjects in the study, Unscheduled visits – see [Section 8.6](#)

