### 8.3.4 Removal of Subjects From Therapy or Assessments

Although the importance of completing the entire clinical study will be explained to the subjects, any subject is free to discontinue his/her participation in the study at any time and for whatever reason, specified or unspecified, and without any prejudice. No constraints are to be imposed on the subject, and when appropriate, a subject may be treated with other conventional therapy when clinically indicated. Investigators or the Sponsor can also withdraw subjects from the clinical study if deemed to be necessary. Data collected up to the time of subject removal will be used.

Reasons for discontinuing study drug include:

- WITHDRAWAL BY SUBJECT  
Subject request (i.e., consent withdrawal)
- PROTOCOL VIOLATION  
Use of non-permitted concurrent therapy (unless discussed and agreed upon with the Investigator and medical monitor)
- NON-COMPLIANCE WITH STUDY DRUG

---

Non-compliance with the study drug or study schedule

- LOST TO FOLLOW-UP
- ADVERSE EVENT

Occurrence of AEs not compatible with the continuation of subject participation in the study, in the Investigator's opinion, or unacceptable to the subject to continue, such as serious immediate-type allergic manifestations, including anaphylactic reaction.

- PREGNANCY
- PHYSICIAN DECISION
- LACK OF EFFICACY
- OTHER
- INTERCURRENT ILLNESS
  - Diagnosis of a malignancy (except curatively treated *in situ* cervical carcinoma or BCC in areas outside of treatment areas studied in this protocol)
  - Any opportunistic infection (such as active TB and other infections whose nature or course suggest an immune-compromised status)

The reason(s) for withdrawal will be documented in the eCRF. Subjects who have been enrolled and treated will not be replaced by another subject.

Subjects who prematurely discontinue study drug will be encouraged to complete the scheduled study visits.

When a subject discontinues study drug, he/she will be fully assessed whenever possible, and followed according to guidelines presented in [Section 8.5.1](#) (Early Termination Visit).

Reasonable efforts will be made to contact subjects who are lost to follow-up. These efforts must be documented in the subject's file.

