#### **8.4.6 Blinding**

All attempts will be made to keep the investigative site staff and subjects blinded throughout the study. Members of the study center staff, including the procedure operator, will not have access to the randomized treatment assignment.

To ensure double-blind administration of study drug, the qualified personnel will dispense all MAL 16.8% cream or vehicle cream treatments, according to the current version of the pharmacy manual provided by the IRT system.

The qualified personnel who dispense the study drug should not be involved with any study assessments, and should not discuss any aspects of study drug dispensation with the subject/caregiver or study staff involved in subject interviews or study assessments.

At the initiation of the study, the study center will be instructed on the method to follow for emergency breaking of the blind. The randomization information for any particular subject may be made available to the Investigator, only in the event of a medical emergency or an AE that necessitates identification of the study drug for the welfare of that participant. Whenever possible, the Investigator or sub-investigator should consult with the medical monitor and the sponsor before breaking the blind.

---

When the blinding code is broken, the reason must be fully documented. If the code is broken by the Investigator, the subject must be withdrawn from the study and must also be appropriately followed for a minimum of 12 weeks after the last dose of study drug. The reporting requirements for unblinding are the same for reporting an SAE. See also [Section 9.2.4.3](#).

The randomization code will remain blinded to all study sites and study team members until completion of the study and after the study database has been locked. Initial treatment period results will be analyzed after all subjects have either completed Visit 6, or have withdrawn or been discontinued from the study before Visit 6. However, personnel from sponsor, CRO, and investigational sites directly involved with the ongoing conduct of the study will not have access to any information that may lead to unblinding for the ongoing recurrence evaluation during the follow-up study.

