### 8.5.1 Early Termination Visit

Subjects may discontinue from the study at any time.

Subjects who prematurely discontinue from the study should undergo final study assessments.

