### Follow-up of Adverse Events

All Investigators should follow-up with subjects with related AEs until the event is resolved or until, in the opinion of the Investigator, the event is stabilized or determined to be chronic. Details of AE resolution must be documented in the eCRF.

Subjects should be followed up for 12 weeks ( $\pm$  5 days) after receiving the last dose of study drug, and any AEs that occur during this time should be reported according to the procedures outlined above.

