10.6.1 Analysis of the Primary Endpoint

The hypothesis test for the primary endpoint can be formally defined as follows:

$$\begin{cases} H_0: \Pi_{MAL} = \Pi_{Vehicle} \\ H_a: \Pi_{MAL} \neq \Pi_{Vehicle} \end{cases}$$

where Π_{MAL} is the proportion of subjects achieving a complete response at 12 weeks after the last MAL DL-PDT and $\Pi_{Vehicle}$ is the proportion of subjects achieving a complete response at 12 weeks after the last vehicle DL-PDT.

The hypothesis test for the primary endpoint will be evaluated on the ITT population at the two-sided significance level $\alpha = 0.00125$. Efficacy will be claimed if the between treatment difference on the primary endpoint is statistically significant with a p-value < 0.00125 . This result will provide an acceptable level of evidence of efficacy, in presence of good internal consistency across primary and secondary endpoints in the absence of a second pivotal study.

The proportion of subjects with complete clearance of all AK lesions treated at each post-baseline analysis visit will be summarized descriptively by treatment groups (overall and by analysis centers). The proportion of subjects with complete clearance of all AK lesions treated at 12 weeks after the last DL-PDT (Visit 6) will be analyzed using the Cochran-Mantel-Haenszel (CMH) test stratified by analysis center (see definition in section 10.6.4.4). No continuity correction will be used. The p-value for the treatment comparison (MAL DL-PDT vs. vehicle DL-PDT) will be calculated from the general association statistic of the stratified CMH test. Difference in proportions between treatment groups and the 99.875% and 95% confidence intervals of the difference will be based on the large sample approximation method for binary data and will be calculated using the method described in the Huiping Zhang "Proportion difference and confidence interval based on Cochran-Mantel-Haenszel method in stratified multi-center clinical trial", 2016, PharmaSUG China 2016, Paper 25 [1]. In addition, the proportion of subjects with complete clearance of all AK lesions treated at 12 weeks after the last DL-PDT (Visit 6) for each treatment group will also be presented.

For the primary analysis, all subjects on the ITT population with missing data for the primary endpoint will be classified as non-responders regardless of treatment allocation (see section 10.6.4.2).

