10.6.4.9 Analysis Visits Definition

Efficacy, safety and other variables will be summarized and analyzed by analysis visit. Analysis visit will be slotted according to the following table (see Table 9) to summarize the data by proper visit.

Table 9 - Analysis Visits Definition

Clinical Visit	Analysis Visit	Analysis Visit Number	Target Study Day
Visit 1	Baseline	1	1
Visit 2	Baseline	1	1
Visit 2b	Baseline	1	1
Visit 3	Week 1	2	8
Visit 4	Week 2-4	3	15
Visit 4b	Week 2-4	3	15
Visit 5	Week 3-5	4	22
Visit 6	Week 14/Final	5	99
Early Termination	Early Termination	6	---

Visit 2b and Visit 4b will occur only in case of incomplete treatment at Visit 2 and Visit 4 respectively. All efficacy assessments performed on Visits 2b and 4b will be assumed to fall at Visits 2 and 4 regardless of actual time.

Early termination visit assessments will be summarized as a separate visit in all by-visit outputs.

Unscheduled visits will be assigned to the same analysis visit of the last scheduled visit (including re-treatment visits) that occurred before the unscheduled visits.

All post-baseline safety assessments will be used for potentially clinically significant value (PCSV) determinations.

For efficacy and safety endpoints, if two or more assessments (include both scheduled and unscheduled assessments) are available for the analysis visits then all assessments will be listed and the following rules will be applied for determining the values to be used for the summary and analyses.

For efficacy endpoints:

Statistical Analysis Plan

- **Baseline Analysis Visit:** in presence of multiple assessments, the last assessment performed before the first DL-PDT treatment (regardless of treatment completion status) will be used for the summaries and analyses.
- **Week 2-4 Analysis Visit:** in presence of multiple assessments, the first assessment performed after the first DL-PDT will be used for the summaries and analyses.
- **Week 14/Final Analysis Visit (where applicable):** in presence of multiple assessments, the first assessment performed after the last DL-PDT will be used for the summaries and analyses.

For safety assessments:

- **Clinical Laboratory Evaluation:** in presence of multiple assessments on an analysis visit, the latest assessment will be used for the summaries and analyses.

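### Protocol 8.3.4 routes subjects who stop study drug both to the scheduled visits and to the Early Termination visit, and the SAP slots ET by label, so a lesion assessment made on time but labelled ET is lost and scored as non-response

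*Protocol*

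**What the plan says.** **Stopping study drug.** Protocol 8.3.4 gives two instructions in succession for the same trigger. The first is "Subjects who prematurely discontinue study drug will be encouraged to complete the scheduled study visits". The second is "When a subject discontinues study drug, he/she will be fully assessed whenever possible, and followed according to guidelines presented in" Section 8.5.1.

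**Leaving the study.** Section 8.5.1 uses a different trigger: "Subjects who prematurely discontinue from the study should undergo final study assessments". It has no text for a subject who stops the cream but stays in the study.

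**Schedule.** Footnote d of Protocol Table 3 is attached to AK mapping, counting and grading, and reads "Should be performed earlier if subject discontinues before Visit 6". It does not say whether drug or study is meant. The Visit 6 column is headed Week 14/ET, and Protocol 9.1.1 pairs Visit 6 with ET when lesion severity and lesion response are recorded.

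**SAP slotting.** SAP 10.6.4.9, Table 9, maps Visit 6 to Week 14/Final (analysis visit 5, target day 99) and Early Termination to its own analysis visit (number 6, no target day). It adds: "Early termination visit assessments will be summarized as a separate visit in all by-visit outputs".

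**Missing data.** In the primary analysis, "all subjects on the ITT population with missing data for the primary endpoint will be classified as non-responders regardless of treatment allocation". Subject partial response follows the same rule (SAP 10.6.3). Percent reduction in lesions uses multiple imputation.

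**The concern.** The non-responder rule is triggered by a missing Visit 6 value, not by stopping treatment. Whether a subject who stops the cream has a Visit 6 value depends on which sentence of 8.3.4 the site follows and on the label it gives the visit. Two subjects with the same course and the same lesions at 12 weeks can then be scored differently: one on outcome, the other as a failure.

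Two things are at stake. Some primary outcomes would be missing although the subject could have been assessed, or was assessed, at the right time. And the response rates would depend to some degree on site habit.

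**Working it through.** **1. Trace one subject through the text.** Take a subject who stops study drug, stays in contact, and has all treated lesions clear 12 weeks after the last DL-PDT received.

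| Route | Visit label | SAP analysis visit | Complete response |
|---|---|---|---|
| Scheduled visits (8.3.4, first instruction) | Visit 6 | 5, Week 14/Final | Responder |
| ET, assessed at 12 weeks | ET | 6, Early Termination | Missing, so non-responder |
| ET, assessed before the Visit 6 window | ET | 6, Early Termination | Missing, so non-responder |

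Rows 1 and 2 differ only in the label. Row 3 is correct as it stands, because an early reading is not the 12-week endpoint. The score differs only for subjects who would have been clear (or at least 75% cleared, for partial response); the others fail on any route.

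**2. Look for a rule that rescues row 2.** None was found.
- SAP Table 9 slots by clinical visit label. Its target day for Week 14/Final is consistent with the endpoint (day 15 + 84 = 99), but no window is applied to ET.
- The multiple-imputation models in SAP 10.6.4.2 use lesion counts from earlier scheduled time points; ET is not named.
- The LOCF rule in the same section does not say whether an ET value may be carried forward.
- The SAP is not uniform on ET. Sections 10.7.4 to 10.7.7 present Visit 6 and ET together, against the statement that ET is separate in all by-visit outputs.

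**3. Reproduce the planned figures** (Protocol 10.2, SAP section 9): 380:190 randomized, 45% against 15%, two-sided alpha 0.00125, 7% non-evaluable.

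Power = Φ{[(p1 − p2) − z·s0] / s1}, with z = 3.227, s0 the pooled and s1 the unpooled standard error.
- Evaluable: 380 × 0.93 = 353.4 and 190 × 0.93 = 176.7. Pooled rate 0.35, s0 = 0.04395, s1 = 0.03771.
- (0.30 − 3.227 × 0.04395) / 0.03771 = 4.19, so power is 99.999%. The plan's figure of more than 90% is confirmed.
- 90% power needs only 142 + 71 = 213 evaluable, or 230 randomized (213 / 0.93, rounded up).
- The number randomized is set by the long-term follow-up target: 380 × 0.93 × 0.45 × 0.70 × 0.90 = 100.2, against about 100.

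**4. Size the effect.** No document gives a rate of stopping study drug or of using the ET route. Let d be the share of an arm scored as failures this way, and assume these subjects would have had the planned response rates. The observed rate is then p × (1 − d), with all 380 and 190 in the denominators.

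| d in MAL / vehicle | MAL | Vehicle | Difference (points) | Power |
|---|---|---|---|---|
| 0 / 0 | 45.0% | 15.0% | 30.0 | above 99.9% |
| 2% / 2% | 44.1% | 14.7% | 29.4 | above 99.9% |
| 7% / 7% | 41.85% | 13.95% | 27.9 | above 99.9% |
| 7% / 0 | 41.85% | 15.0% | 26.9 | above 99.9% |
| 0 / 7% | 45.0% | 13.95% | 31.1 | above 99.9% |
| 15% / 0 | 38.25% | 15.0% | 23.3 | 99.7% |

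With 7% in both arms, about 12 MAL responders (380 × 0.45 × 0.07) and 2 vehicle responders (190 × 0.15 × 0.07) are rescored. The 45% is planned for subjects who receive two sessions, so applying it to subjects who stopped after one may overstate the effect.

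**The case against.** **The two sentences can be read in sequence:** complete the visits if willing, and have final assessments on leaving the study. Section 8.5.1 fits that reading, and nothing says that an ET visit cancels later visits for a subject who still attends. This is fair, and many sites may act this way. But 8.3.4 does not say so; it ties the Early Termination reference to stopping study drug, and footnote d leaves the word open.

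**A subject seen at 12 weeks would normally be recorded as Visit 6,** so the in-window ET case may be rare. Also fair, and the size is therefore uncertain. But the combined Visit 6/ET column invites either label, and the SAP then separates them by label alone.

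**The scoring looks conservative, and the sensitivity analyses are extensive.** Losing responders equally in both arms lowers the difference, and the plan already has multiple imputation, tipping-point, LOCF, observed-case and per-protocol analyses. That limits the harm. It does not justify setting aside an outcome measured at the right time.

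**Stronger readings that the documents do not support:**
- *That the loss falls mainly on MAL.* No stopping rate is given for either arm. Protocol 6.2.1 describes DL-PDT as almost painless, and 6.3 says that even with conventional PDT early termination of illumination was rarely needed.
- *That suspected sensitization leads to an early ET visit.* Protocol 9.4.4 stops the drug, then provides for rechallenge and possible resumption, so the subject is not thereby out of the study.
- *That every ET assessment should count as Visit 6.* Those made before the window are rightly excluded.
- *That the 12-week contact already supplies the outcome.* Under Follow-up of Adverse Events, "Subjects should be followed up for 12 weeks" concerns adverse events; it does not require lesion mapping.
- *That unblinded subjects should be handled in the same way.* Protocol 8.4.6 says "the subject must be withdrawn from the study and must also be appropriately followed for a minimum of 12 weeks". Overriding that could also bring readings by an unblinded investigator into an endpoint that 9.1 requires to be read blind.

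**Conclusion.** The point holds in a limited form and is a cheap improvement. The protocol does not separate stopping study drug from leaving the study, and the SAP's slotting by label discards a lesion assessment that meets the 12-week definition if it is labelled ET. Complete response and partial response are affected. Percent reduction in lesions is not scored this way, because missing counts are imputed.

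The consequence is avoidable missing data and a somewhat site-dependent estimate. If the full planned 7% were lost this way in both arms, the expected difference would be 27.9 instead of 30.0 points; a 2% loss would give 29.4. These figures rest on assumed shares and on the planned response rates applying to subjects who stop. A reader might infer a threat to power; the calculation rules that out, since power stays at about 99.7% or more even with a 15% loss in MAL only. The direction of any imbalance between arms cannot be settled from the documents.

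**What to change.** 1. **Protocol 8.3.4, 8.5.1 and footnote d of Table 3** (repeated in SAP Table 1): reconcile them so that stopping study drug is distinct from leaving the study. For subjects who remain in the study, state that the Visit 6 lesion assessment is still collected 12 weeks after the last DL-PDT actually received. Reserve the ET visit for subjects leaving the study.
2. **SAP 10.6.4.9:** slot any ET-labelled lesion assessment made within the Visit 6 window (84 days, −2/+28, after the last DL-PDT; that is, days 82 to 112 after it) to Week 14/Final. Keep other ET assessments separate, and state in 10.6.4.2 whether they enter the multiple-imputation and LOCF analyses. The non-responder rule is otherwise unchanged.
3. **Protocol 8.4.6:** flag the combination of withdrawal and 12-week follow-up for the sponsor to reconcile with the sections above. No change to the withdrawal rule is proposed here.

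The cost is a few sentences in the protocol and SAP, by the update route in SAP section 11, and the effort of following a few off-treatment subjects to Visit 6.

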#### 8.3.4.1 Pregnancy

Subjects will be instructed that known or suspected pregnancy occurring during the study should be confirmed and reported to the Investigator. **If a subject becomes pregnant, the Investigator must withdraw the subject from the study without delay. The subject must not receive any further study drug.** Pregnancy is not to be considered as an AE; however, it must be monitored and reported as described in [Section 9.2.4.4](#).

The Investigator must:

- 
- Follow the procedures for reporting/follow-up of a pregnancy within 24 hours (see [Section 9.2.4.3](#)) of receipt of the information.
  - Complete as fully as possible the applicable Pregnancy Surveillance Form(s) (see [Section 9.2.4.3](#))
  - Monitor and record the progress of the pregnancy until its outcome. Contact the subject's regular physician (general practitioner or gynecologist) or hospital staff to obtain further details and ask for regular follow-up information.
  - Provide tri-monthly updates until the final outcome of the pregnancy. If the subject can no longer be reached (lost to follow-up), documentation of the non-response/contact with 2 phone calls and a letter (certified with return receipt) is required.
  - If the pregnancy leads to an abortion (i.e., voluntary abortion, spontaneous abortion, or therapeutic abortion), *in utero* death, or congenital anomaly, follow the procedure for declaration of/reporting an SAE ([Section 9.2.4.3](#)).

The investigator should also be notified of pregnancy occurring during the study (and within 12 weeks [ $\pm$  5 days] after the last dose of study drug) but confirmed after completion of the study. In the event that a subject is subsequently found to be pregnant after inclusion in the study, any pregnancy will be followed to term, and the status of mother and child will be reported to the sponsor after delivery.

Full details will be recorded on the withdrawal page (exit form), or an SAE report will be completed if the subject has completed the study.

## 8.4 Investigational Products

“Study drug” refers to methyl aminolevulinolate hydrochloride 16.8% cream (CD06809-41) or vehicle cream for the purpose of this double-blind study.

### 8.4.1 Investigational Products Administered

Study drug will be supplied as a cream, which is cream to pale yellow in color in a 2 g aluminum tube.

Vehicle cream will be supplied as a cream, which is cream to pale yellow in color in a 2 g aluminum tube.

Health care professionals should wear nitrile gloves when applying and removing MAL 16.8% cream.

